## **8.3 Criteria before the open-label treatment phase**

### **8.3.1 Inclusion Criteria before the open-label treatment phase**

Subjects who meet the following criterion will enter the open-label treatment phase.

1. Subjects who have completed the 6-week study treatment and all scheduled assessments at Visit 6 in the double-blind treatment phase, and who are considered eligible by the Investigator with no safety concerns

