7.6.2.1.2 Time to Treatment Discontinuation

The time to treatment discontinuation for the double-blind treatment phase and the open-label treatment phase will be analyzed using the Kaplan-Meier method for m ITT population or the open-label population respectively. The time to treatment discontinuation will be listed.

- All cause discontinuation will be considered as an event in both the double-blind treatment phase and the open-label treatment phase.
- Subjects who completed the double-blind treatment phase, subjects will be censored at the final application date of the study medication of the double-blind treatment phase.
- Time to treatment discontinuation for the double-blind treatment phase will be determined as the final application date in the double-blind treatment phase – the initial application date in the double-blind treatment phase + 1.
- Subjects who completed the open-label treatment phase, subjects will be censored at the final application date of the study medication of the open-label treatment phase.
- Time to treatment discontinuation for the open-label treatment phase will be determined as the final application date in the open-label treatment phase – the initial application date in the open-label treatment phase + 1.

Kaplan-Meier estimate for 25, 50, and 75 percentiles for time to treatment discontinuation and Kaplan-Meier plots by treatment group will be provided. Additionally, in summary for the double-blind treatment phase, number and percentage of subjects who stay the study for 42 days and its 95%CI will be provided, and in summary for the open-label treatment phase, number and percentage of subjects who

stay the study up to 28 weeks (196 days), and 52 weeks (364 days) and its 95%CI will be provided,

These will be repeated by country. In this case, number and percentage of subjects who stay the study up to 52 weeks (364 days) and its 95%CI will be summarized only for Japan.

The mock SAS code for Kaplan-Meier analysis is given below:

```
proc lifetest data=&ads plots=survival(atrisk);  
strata trt01p;  
time tte*censor(1);  
ods output quartiles=mst;  
run;  
* tte is the variable for time to discontinuation;  
* if completer then censor=1; else censor=0;
```

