7.9 Interim Analysis, Interim Data Summary, and Final Analysis

An unblinded interim analysis for futility will be performed after 50% of target number of subjects complete or prematurely discontinue the double-blind treatment phase. The interim analysis will be performed on the change in PANSS total score from baseline in the mITT population. If the conditional power based on the treatment differences in PANSS total score is less than the futility criteria of 8%, the study may be terminated early. Otherwise, the study will be continued. The interim analysis will be conducted based on the charter for the interim analysis and an interim analysis plan, separately from this document.

Apart from the formal interim analysis, after all subjects have completed the double-blind treatment phase or prematurely terminated the study, the efficacy and safety data up to 6 weeks will be analyzed. After all subjects have completed at Visit 108 (Open-Week 24) in the open-label treatment phase or discontinued from the study, the study data will be analyzed for the purpose of the regulatory submission before the database lock.

The unblinded analysis after the completion of the double-blind treatment phase will be limited for the analyses for this phase, based on the database for double-blind treatment phase (EDC for this phase), and using the mITT, PP, safety and PK populations. These analysis populations and important protocol deviations in the double-blind treatment phase will be determined in a blinded data review prior to unblinding. However only subject assignment to PK population in the double-blind treatment phase will be finalized after unblinding, and PK data is obtained and reviewed by the study team.

After completion of Visit 108, the database for double-blind treatment phase and open-label treatment phase will be combined to analyze the DSP-5423P treatment period using the DSP-5423P dosed population as well as the open-label population. The analysis will be limited for data from Visit 101 (Open-Week 1) to Visit 108 (Open-

Week 24) including discontinuation and unscheduled visits during Visit 101 to 108. Adverse events and concomitant medications occurred or started on or after Open Day 177 or later will not be included. The DSP-5423P dosed population and the open-label population and important protocol deviations for the open-label treatment phase up to Visit 108 will be determined prior to the data lock for the interim data summary.

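### The 42-, 196- and 364-day retention counts are undefined and, as crude counts, would miss on-schedule completers; the mock censoring code would turn subjects ongoing at the Visit 108 cut into discontinuations

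*SAP*

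**What the plan says.** SAP 7.6.2.1.2 makes all-cause discontinuation the event and uses Kaplan-Meier in both phases. For the double-blind phase: "Time to treatment discontinuation for the double-blind treatment phase will be determined as the final application date in the double-blind treatment phase" minus the initial application date, plus 1. The open-label definition has the same form: "Time to treatment discontinuation for the open-label treatment phase will be determined as the final application date in the open-label treatment phase" minus the initial application date, plus 1. For double-blind completers, "subjects will be censored at the final application date of the study medication of the double-blind treatment phase"; open-label completers are treated in the same way.

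After listing the Kaplan-Meier percentiles and plots, the section asks in addition for the "number and percentage of subjects who stay the study for 42 days" with a 95% CI, and for those who "stay the study up to 28 weeks (196 days), and 52 weeks (364 days") in the open-label phase. It does not say whether this is a crude proportion or a survival estimate, how a completer with a shorter time is classified, or how the CI is computed. The mock code outputs quartiles only. Its comment defines the status variable: "if completer then censor=1; else censor=0".

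The final-visit windows in Protocol Tables 3 to 5 are Day 40-43 (Visit 6), Open-Day 190-204 (Visit 109, the last open-label visit outside Japan) and Open-Day 351-379 (Visit 112, the last in Japan). Protocol 8.3.1 admits to the open-label phase "Subjects who have completed the 6-week study treatment and all scheduled assessments at Visit 6 in the double-blind treatment phase" who raise no safety concern. It sets no minimum number of days.

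For the submission analysis, SAP 7.9 states: "The analysis will be limited for data from Visit 101 (Open-Week 1) to Visit 108" (Open-Week 24). SAP 7.2 provides an Ongoing row in the open-label disposition table for the interim data analysis.

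**The concern.** The milestones are exact multiples of seven days, while completion is governed by visit windows that open before those days. A subject can do everything the protocol asks and still have a time on treatment below the milestone. If retention means time at or above the milestone, that subject is tabulated with the drop-outs, and the percentage reflects visit scheduling as well as discontinuation.

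The censoring code raises a second issue. It has two states, completer and everyone else. At a data cut before the phase ends there is a third state, ongoing, and the code puts it with the events. Time to open-label discontinuation is a listed secondary endpoint (Protocol 6.2), so a submission-cut curve built that way would misreport it.

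**Working it through.** **1. The milestones.** 6 × 7 = 42, 28 × 7 = 196 and 52 × 7 = 364, as the SAP states.

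**2. Times an on-schedule completer can have.** Day 1 is the first application, so a last patch on Day *d* gives a time of *d* days. Two cases are shown: last patch on the visit day (time = *d*), and last patch the day before (time = *d* − 1). The second is plausible at Visit 6. Key Week 6 assessments must precede the first open-label patch (Protocol Table 3, note g), so if that patch goes on at the visit, the last double-blind patch was the previous day's.

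| Milestone | Window | Times, last patch on visit day | Visit days falling short | Times, last patch day before | Visit days falling short |
|---|---|---|---|---|---|
| 42 days | Day 40-43 | 40-43 | 40-41: 2 of 4 | 39-42 | 40-42: 3 of 4 |
| 196 days (outside Japan) | Open-Day 190-204 | 190-204 | 190-195: 6 of 15 | 189-203 | 190-196: 7 of 15 |
| 364 days (Japan) | Open-Day 351-379 | 351-379 | 351-363: 13 of 29 | 350-378 | 351-364: 14 of 29 |

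The windows for Visits 3, 4 and 5 centre on Days 8, 15 and 29, that is 7 × week + 1. On that pattern the nominal Visit 6 is Day 43, and its window of 40-43 allows early attendance only.

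**3. Where the 196-day row applies.** Japanese subjects continue past Visit 109 to Visit 112, so an early Visit 109 does not end their treatment. Summing the site counts in SAP Appendix II, Japan has 25 + 28 + 42 + 29 + 24 + 16 = 164 of 582 randomized subjects (28%). The other 418 (72%) are outside Japan. These are randomized subjects, not open-label entrants.

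**4. Effect on a crude 42-day count (illustration).** Assume a completion rate of 133/167 = 79.6%, taken from the sample-size figures in Protocol 15.1; the plan does not state it as a completion rate. The crude figure is 79.6% × (1 − share of completers falling short):

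| Share of completers below 42 days | Crude retention |
|---|---|
| 10% | 71.7% |
| 25% | 59.7% |
| 50% (uniform attendance, last patch on visit day) | 39.8% |
| 75% (uniform attendance, last patch day before) | 19.9% |

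The share falling short is not in the documents.

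**5. Effect on Kaplan-Meier.** The estimate drops only at events. A completer censored at 39 to 41 days leaves the risk set without lowering the curve. Simulating the two uniform-attendance cases, with all discontinuations before the first completion, gave 79.6% at Day 42, equal to the true completion rate. One caution is that few subjects may still be at risk on Day 42 itself.

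**6. The Visit 108 cut.** The code treats status 1 as censored and gives it to completers only. The earliest completing visit is 109. On data limited to Visit 108, and with completion judged on those data, no subject is a completer, so everyone who has not discontinued becomes an event. The text makes discontinuation the event, which an ongoing subject has not had, but it gives no censoring rule for ongoing subjects. The Visit 108 window is Open-Day 162-176, and 196 − 176 = 20, so 196 days lies beyond any in-window time at that cut.

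**The case against.** The strongest reply is that the SAP never writes a rule of time at or above the milestone. The section's declared method is Kaplan-Meier, completers are explicitly censored, and the retention figure sits with the Kaplan-Meier percentiles. Read as the survival estimate at Day 42, it does not count completers as failures. This stands to the extent that a miscount is not established. It does not settle the matter: a survival estimate does not supply a number of subjects, the figure is requested in addition to the Kaplan-Meier output, and the code requests no estimate at a time point. A crude count is the natural reading, though not the only one.

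It is also fair that the code is labelled mock, that its comment is shorthand, and that the text and SAP 7.2 both point to ongoing subjects not being events. A careful programmer may code it correctly. But no sentence says to censor them, and the one explicit status rule does the opposite.

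A reader might infer that the named secondary endpoint is understated because of the windows. The documents do not support that: its curves and percentiles censor completers, and 42-day retention is not a protocol endpoint.

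**Conclusion.** The point holds as a defect of definition with a foreseeable wrong result. Under a crude count, compliant completers would be recorded as not retained whenever the final visit falls on the window days listed above. Those day counts are exact. The percentage of subjects affected is unknown. Retention of 20-40% at 42 days, or a loss of 40-48% of completers at the later milestones, might be inferred, but that needs uniform attendance across each window, which has no source. The 42-day range also needs an assumed completion rate of about 80%, and the 196-day loss cannot apply in Japan.

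The coding point is conditional on the analysis being run at the Visit 108 cut with the rule as written. A reader might infer that the submission curve will fall towards zero near Open-Week 24; that follows only under both conditions, and the SAP does not expressly schedule this analysis for that cut. Nor do the documents impose a general data stop at Open-Day 176: the exclusion from Open-Day 177 in SAP 7.9 is stated for adverse events and concomitant medications, while other data are limited by visit. The 196-day figure is still not meaningful there.

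The effect is confined to descriptive retention summaries and, if produced, the submission-cut curve. The primary analysis and the final-analysis Kaplan-Meier curves and percentiles are not affected.

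**What to change.** In SAP 7.6.2.1.2:

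- Define the retention statistic. Either count a subject as retained if the CRF disposition for the phase is completed or time on treatment reaches the milestone, or report the Kaplan-Meier estimate at the last day before the completion window opens (Day 39, Open-Day 189, Open-Day 350). Name the CI method.
- If the disposition rule is used, apply the 52-week figure to Japan only in the overall table as well. The Japan-only limit is now stated only for the by-country output, and a 28-week completer elsewhere should not count as retained at 52 weeks.
- Set event = discontinued and censored = completed or ongoing, state the censoring date for ongoing subjects, and change the code comment to match.
- At the Visit 108 cut, replace 196 days by a day before that visit's window opens, for example Open-Day 161.

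The cost is a few sentences of SAP text and one line of code, with no new data.

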#### **15.3.5.3.2 Open-label treatment phase**

The time to treatment discontinuation from the initial application in the open-label treatment phase will be analyzed using the Kaplan-Meier method for the open-label population. The Kaplan-Meier curves will be shown overall and by treatment group in the double-blind treatment phase.

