5.3 Open-label population

The open-label population will consist of all subjects who apply DSP-5423P at least once in the open-label treatment phase.

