7 STATISTICAL METHODS

7.1 General Principles

All data processing, summarization and analyses will be performed using the SAS enterprise 5.1 (SAS 9.3) or higher on SAS hosted environment, unless otherwise specified.

Unless otherwise specified, data will be displayed using the following treatment group labels, in the order presented:

- 1) Double-blind treatment phase
 - Placebo group is labelled as PLCB
 - DSP-5423P 40 mg group is labelled as 40MG
 - DSP-5423P 80 mg group is labelled as 80MG
 - Combined group of DSP-5423P 40 mg and 80 mg group is labelled as Active
 - Combined group of DSP-5423P 40 mg, 80 mg and placebo group is labeled as

Statistical Analysis Plan

Version: 2

Study No. D4904020

Overall

Treatment groups for tables and figures

	PLCB	40MG	80MG	Active	Overall
Efficacy	Y	Y	Y		
Safety	Y	Y	Y	Y	
PK		Y	Y		
Others *	Y	Y	Y	Y	Y

* subject disposition, analysis populations, demographics, psychiatric history, prior and concomitant medications, treatment compliance, treatment exposure. Active group will not be displayed for efficacy analyses.

2) Open-label treatment phase and DSP-5423P treatment period

For tables and figures for the open-label treatment phase and DSP-5423P treatment period, subjects are summarized based on the treatment group in the double-blind treatment phase as, PLCB-to-FLEX DOSE, 40MG-to-FLEX-DOSE, 80MG-to-FLEX DSOE, Active-to-FLEX DOSE, and Overall-to-FLEX DOSE. PK analysis for the open-label treatment phase will be based on the latest dose before the PK sampling.

All data collected will be presented in listings by treatment group, subject, visit and date, unless otherwise specified.

Data will be presented in summary tables by treatment group, assessment and visit (where applicable).

Continuous parameters will be summarized using number of subjects (n), mean, standard deviation (SD), median, minimum (min), and maximum (max) values. Mean and median will be displayed to one more decimal place than the original value; min and max will keep the same number of decimal places. SD will be displayed to two more decimal places from the original value. For the case of CGI-S, another decimal point will be added to mean, median, and SD following the rules above. With regard to Pharmacokinetics parameters, Geometric Mean will be displayed to one more decimal place than the original value, and CV% and Geometric CV% will be done to one decimal place. M1/blonanserin will be displayed to three decimal place.

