7.2 Subject Disposition and Data Sets Analyzed

Subject disposition will be listed and summarized by treatment group and overall, and will include the number and percentage of subjects for the double-blind treatment phase and the open-label treatment phase, the denominator of the percentage will be the number of randomized subjects and the number of the open-label population, respectively. Summaries of subject disposition will be repeated by country for both treatment phases.

For the double-blind treatment phase, the following information will be reported:

- informed consent obtained,
- not enrolled in the wash-out phase; with breakdown by reason for disposition,
- enrolled in the wash-out phase,
- not randomized; with breakdown by reason for disposition,
- randomized,

Statistical Analysis Plan

Version: 2

Study No. D4904020

- not treated in the double-blind treatment phase; with breakdown by reason for disposition,
- treated in the double-blind treatment phase,
- completed the double-blind treatment phase,
- discontinued from the double-blind treatment phase; with breakdown by reason for disposition.

For the open-label treatment phase, the following information will be reported:

- completed the double-blind treatment phase,
- not treated in the open-label treatment phase; with breakdown by reason for disposition,
- treated in the open-label treatment phase,
- Ongoing; displayed ONLY for interim data analysis,
- completed the open-label treatment phase,
- discontinued from the open-label treatment phase; with breakdown by reason for disposition.

The number and percentage of subjects who included in each analysis population will be summarized for the double-blind treatment phase and the open-label treatment phase, where the denominator of the percentage will be the number of randomized subjects and the number of subject treated at least once in the open-label treatment phase, respectively. These summaries will be repeated by country.

For the double-blind treatment phase, the following analysis populations are of interest:

- mITT population,
- PP population,
- Safety population,
- PK population.

For the open-label treatment phase, the following analysis populations are of interest:

- Open-label population,
- DSP-5423P dosed population,
- PK population.

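### The 52-week open-label retention figure is limited to Japan only in the by-country tables, so the pooled and by-arm versions include countries where open label ends at 28 weeks

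*SAP*

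**What the plan says.** Time to treatment discontinuation in the open-label phase is a listed secondary endpoint (Protocol 6.2, SAP 3.2). SAP 7.6.2.1.2 analyses it by Kaplan-Meier in the open-label population. Discontinuation for any cause is the event. For those who complete the phase, "subjects will be censored at the final application date of the study medication of the open-label treatment phase".

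The same section adds two landmarks to the open-label summary, a count and percentage of subjects who "stay the study up to 28 weeks (196 days), and 52 weeks (364 days) and its 95%CI will be provided". It then says the outputs are repeated by country, and that in this case the number and percentage who "stay the study up to 52 weeks (364 days) and its 95%CI will be summarized only for Japan".

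The surrounding definitions carry no country limit:

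- SAP 5.3: "The open-label population will consist of all subjects who apply DSP-5423P at least once in the open-label treatment phase".
- SAP 7.1 gives open-label tables a column for each double-blind arm, plus "Active-to-FLEX DOSE, and Overall-to-FLEX DOSE".
- Protocol 15.3.5.3.2: "The Kaplan-Meier curves will be shown overall and by treatment group in the double-blind treatment phase". The protocol asks for no landmarks; these are a SAP addition.

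The planned duration differs by region. The Protocol synopsis (Duration of Treatment) gives 28 weeks outside Japan and 52 weeks in Japan. The last open-label visit outside Japan has a window of Open-Day 190 to 204 (Protocol Table 4).

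**The concern.** The Japan limit is attached to the by-country repeat. Nothing in either document extends it to the main table, so as written the pooled, Active and by-arm columns each carry a 364-day figure. Their population includes subjects who, by design, cannot be on treatment at day 364 even if they complete.

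The section also does not name the estimator for the landmarks. It opens with Kaplan-Meier and censors completers, which favours a Kaplan-Meier estimate at days 196 and 364. But the landmark is worded as a count and percentage, and the mock code outputs only the quartiles. It does not request survival at either day, so a programmer could produce a crude proportion and still follow the text.

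At stake is how one long-term retention figure is read. It would be labelled as 52-week retention of the whole open-label population, or of an arm, when the 52-week information comes from one country.

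**Working it through.** **Inputs from the documents**

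- Randomised subjects by country, summed from SAP Appendix II: Japan 164; Korea 21, Taiwan 46, Malaysia 169, Philippines 69, China 28, Russia 39, Ukraine 46.
- Open-label duration: 196 days outside Japan, 364 days in Japan.
- Censoring of completers at final application (SAP 7.6.2.1.2).

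**Step 1. Check the plan's total.** Outside Japan: 21 + 46 + 169 + 69 + 28 + 39 + 46 = 418. With Japan: 418 + 164 = 582, which matches Appendix II. Shares: 164/582 = 28.2% and 418/582 = 71.8%. These are shares of randomised subjects. The documents do not give the number entering open label by country, so using them for the open-label population is an assumption.

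**Step 2. Kaplan-Meier reading (favoured).** Non-Japanese completers are censored by about Open-Day 204. The pooled estimate is then approximately

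S(364) = [w × S_J(196) + (1 − w) × S_O(196)] × S_J(364)/S_J(196),

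where J is Japan, O is the other countries and w is Japan's share. The last factor uses Japanese subjects only.

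For illustration, assume constant hazards, w = 0.282 and 52-week Japanese retention of 60%. Then S_J(196) = 0.60^(196/364) = 0.760 and S_J(364)/S_J(196) = 0.60^(168/364) = 0.790. The hazard elsewhere is expressed as the 52-week retention it would imply.

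| Assumed elsewhere | S_O(196) | Bracket | Pooled S(364) |
|---|---|---|---|
| 60% (same hazard) | 0.760 | 0.760 | 0.760 × 0.790 = 60% |
| 40% | 0.611 | 0.653 | 0.653 × 0.790 = 52% |
| 80% | 0.887 | 0.851 | 0.851 × 0.790 = 67% |

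With equal hazards the estimate is right. With unequal hazards it is neither Japan's 60% nor a 52-week figure for any population that was treated for 52 weeks.

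**Step 3. How many subjects support the later part.** Even allocation gives 164/3 = 54.7 Japanese subjects per arm. Assume 60–80% enter open label and 60–80% of those are still on treatment at week 28. The risk set is then 54.7 × 0.36 = 20 to 54.7 × 0.64 = 35 per arm, or 164 × 0.36 = 59 to 164 × 0.64 = 105 pooled. Both rates are assumed, not documented.

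**Step 4. Crude reading (less likely).** Non-Japanese completers count as not retained, so the pooled percentage is Japan's share × Japanese 52-week retention and cannot exceed the share. With 60% retention assumed, a 28.2% share gives 0.282 × 0.60 = 17%. Assumed shares of 20% and 40% give 12% and 24%.

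**The case against.** The best defence is that Kaplan-Meier is made for this. Non-Japanese completers leave the risk set because their planned treatment ends, not because of how they are doing. They contribute valid information up to about day 204, and with similar hazards the estimate is unbiased. That stands. What remains is that the later part comes from a single country, and the documents give no basis for assuming similar hazards.

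A second defence is that the remedy largely exists. A Japan-only 52-week figure is already planned in the by-country repeat. SAP 7.2 also provides that "Summaries of subject disposition will be repeated by country for both treatment phases", and the mock code ("proc lifetest data=&ads plots=survival(atrisk") puts numbers at risk on the plots. This is true and keeps the point small. It does not correct the pooled figure, and the plotted numbers at risk are stratified by arm, not by region.

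A reader might infer more than the documents support:

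- **A large downward bias.** The 12–24% figures need the crude reading and assumed rates. Censoring of completers points the other way.
- **Completers miscounted because visit windows open before days 196 and 364.** This has no force under Kaplan-Meier. Window days are not subjects, and the documents do not say how final applications fall within the windows.
- **A table that conceals the problem.** Table shells are not in the documents, so labels and footnotes cannot be judged.
- **An effect on the submission summary.** SAP 7.9 cuts that summary at Visit 108 (Open-Week 24), so no 364-day figure can arise there.

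**Conclusion.** The concern holds as a minor point of specification. The Japan limit on the 364-day figure should cover the main table and does not. On the Kaplan-Meier reading there is no fixed bias. The pooled and by-arm values join all-country retention to about Open-Day 204 with Japan-only retention afterwards, so they do not describe 52-week retention of the population or arm named. On the crude reading they are capped by Japan's share of the open-label population, about 28% if the randomised mix carries over.

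Only the 28%/72% split of randomised subjects is documented. The retention rates, risk-set sizes and open-label mix used above are assumptions. The output is descriptive, has no planned test, and arises only in the final analysis. The primary analysis is unaffected.

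**What to change.** In SAP 7.6.2.1.2, state that:

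- the 364-day landmark is reported for Japanese subjects only in every table, overall and by arm;
- the 196-day landmark is reported for all countries;
- both are Kaplan-Meier estimates with 95% CI, with the number at risk shown beside each.

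This takes one or two sentences and no new data. It extends a limit the SAP already applies by country, and it does not conflict with the protocol, which asks only for the curves. The small downside is losing a pooled 52-week number.
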